ComRes5	0=NO 1=YES 8=DON'T KNOW 9=REFUSE	(Since discharge from the hospital after your/his/her stroke) How about exercise classes that are open to the general public, like ones offered at a church or fitness center?	
ComRes6	0=NO 1=YES 2=DOES NOT SMOKE 8=DON'T KNOW 9=REFUSE	(Since discharge from the hospital after your/his/her stroke, how about) programs to help you quit smoking?	
ComRes7	0=NO 1=YES 8=DON'T KNOW 9=REFUSE	(Since discharge from the hospital after your/his/her stroke, how about) a falls prevention program that teaches you how to improve your balance and strength so you don't fall?	
ComRes8	0=NO 1=YES 8=DON'T KNOW 9=REFUSE	(Since discharge from the hospital after your/his/her stroke, how about) programs that provide meals – either delivered to your house or a central location like a church or community center?	
ComRes9	0=NO 1=YES 8=DON'T KNOW 9=REFUSE	(Since discharge from the hospital after your/his/her stroke, how about) a support group for stroke survivors? IN NOTE: these are groups that provide social support, information, and resources for stroke survivors	
ComRes10	0=NO 1=YES	(Since discharge from the hospital after your/his/her stroke, how about)	

Application - IRB00035998			
	8=DON'T KNOW 9=REFUSE	medication assistance or management services to help pay for the medications or to help understand and manage the medications? IN NOTE: management services are usually offered by pharmacists.	
ComRes11	0=NO 1=YES 8=DON'T KNOW 9=REFUSE	(Since discharge from the hospital after your/his/her stroke, how about) transportation services to get you to your healthcare appointments or community activities? IN NOTE: THIS DOES NOT INCLUDE REGULAR PUBLIC	
ComRes12	0=NO 1=YES 8=DON'T KNOW 9=REFUSE	TRANSPORTATION (Since discharge from the hospital after your/his/her stroke, how about) support services for your family or caregivers? IN NOTE: these are groups or services that provide social support, information, and resources for caregivers/family members of storke survivors?	
ComRes13	0=NO (GO TO EDUC) 1=YES (GO TO COMRES14) 8=DON'T KNOW (GO TO EDUC) 9=REFUSE (GO TO EDUC)	Are there any other services you've/he's/she's used that I haven't mentioned?	
ComRes14	SPECIFY OTHER OPEN TEXT [250 CHAR]	What are those?	

Educ	1=8TH GRADE OR LESS 2=SOME HIGH SCHOOL, BUT DID NOT GRADUATE 3=HIGH SCHOOL GRADUATE OR GED 4=SOME COLLEGE OR 2- YEAR DEGREE 5=4-YEAR COLLEGE GRADUATE 6=MORE THAN 4-YEAR COLLEGE DEGREE 8=DON'T KNOW 9=REFUSE	What is the highest grade or level of school that you/he/she have/has completed?	
PROMIS_INTRO	EMPTY	These last few questions are about your health and how you have been feeling.	
Global01	1=Excellent 2=Very good 3=Good 4=Fair, or 5=Poor	In general, would you say your health is	
Global02	1=Excellent 2=Very good 3=Good 4=Fair, or 5=Poor	In general, would you say your quality of life is	
Global03	1=EXCELLENT 2=VERY GOOD 3=GOOD 4=FAIR, OR 5=POOR	In general, how would you rate your physical health? (Would you say)	
Global04	1=EXCELLENT 2=VERY GOOD 3=GOOD 4=FAIR, OR 5=POOR	In general, how would you rate your mental health, including your mood and your ability to think? (Would you say)	
Global05	1=EXCELLENT 2=VERY GOOD 3=GOOD 4=FAIR, OR 5=POOR	In general, how would you rate your satisfaction with your social activities and relationships? (Would you say)	

Application - IRB0003.			
Global09	1=EXCELLENT 2=VERY GOOD 3=GOOD 4=FAIR, OR 5=POOR	In general, please rate how well you carry out your usual social activities and roles. This includes activities at home, at work and in your community, and responsibilities as a parent, child, spouse, employee, friend, etc. (Would you say)	
Global06	1=Completely 2=Mostly 3=Moderately 4=A little, or 5=Not at all	To what extent are you able to carry out your everyday physical activities such as walking, climbing stairs, carrying groceries, or moving a chair? Would you say	
Global10	1=Never 2=Rarely 3=Sometimes 4=Often, or 5=Always	In the past 7 days, how often have you been bothered by emotional problems such as feeling anxious, depressed or irritable? Would you say	
Global08	1=None 2=Mild 3=Moderate 4=Severe, or 5=Very severe	In the past 7 days, how would you rate your fatigue on average? Would you say	
Global07	ENTER NUMBER (RANGE 0-10)	Picture a scale from 0 to 10, with zero being no pain and ten being the worst imaginable pain. In the past 7 days, how would you rate your pain on average?	
THANK_YOU		Thank you. That's the end of the survey. Goodbye.	

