- 5). Phase 2: Using Claims, the Sustainability analyses compared outcomes in hospitals randomized to deliver the INV in Phase 1 with outcomes among those that sustained the intervention (SUS) in Phase 2 for mortality; health care utilization; (emergency department visits, admissions to skilled nursing facilities/inpatient rehabilitation

Application - IRB00035998

facilities); and use of transitional care management billing codes. We will use claims data from multiple payer sources up to 12 months after stroke hospitalization.

Data Collected for Ancillary Studies:

- 1) Analysis of individual, organizational, and community factors affecting implementation of COMPASS through supplemental funding (CTSI Award lead by Co-I [name]). This pilot project will contribute to a process evaluation of our Phase1, intervention-randomized health systems adopting COMPASS.
- 2) An exploratory analysis that compares patient clinic return rate and use of services to physical locations of patients and services (i.e. distance and drive times to/from clinics and community resources).
- 3) At the 90 day survey, we will also use the PROMIS Global-10 instrument that assesses general domains of health and functioning including overall physical health, mental health, social health, pain, fatigue, and perceived quality of life. These are similar in nature to our primary outcome, the SIS-16.

Hospital Performance Metrics (to support participating sites in delivery of the intervention):

1) Evaluate compliance with the new model of post-acute stroke care by exploring quality indicators among intervention hospitals, (e.g., proportion of patients called within 2 days after hospital discharge; proportion of patients seen by an advanced practice provider [MD/NP/PA] within 7 to 14 days from hospital discharge; and proportion of eligible patients receiving home or outpatient rehabilitation therapy).

Methods and Measures

Study Design

The COMPASS Study is a pragmatic, cluster-randomized trial of 41 hospitals in North Carolina designed to determine the effectiveness of a model of post-acute stroke care (i.e. the COMPASS Intervention) compared with usual care (Control).

Study Setting

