At 90 Days, stroke survivors will receive a phone call from the Carolina Survey Research Lab (CSRL). CSRL will follow a telephone script which includes consent (Appendix 10) and conduct blinded assessments (Appendix 23 and 24). If the patient prefers s/he can request that a proxy answer questions and provide verbal consent and HIPAA Authorization on her/his behalf. In the event contact is never made with the patient by phone or connection is lost (e.g. the number is not in service, no one answers the phone calls, call is answered but is disconnected prior to the researcher sharing the reason for calling, or there is loss of connection during the call) we will mail an abbreviated version of the survey with a letter explaining the survey purpose (Attachment 25). We will also include a self-addressed envelope with prepaid postage to the patient to gather responses via paper survey. This abbreviated survey contains the SIS-16, global health rating scale and blood pressure questions. (Note: this is identical to the Control group)

Approximately one year later the study will acquire claims data from Medicare, Medicaid, State Insurance Plan, and Blue Cross Blue Shield. We plan to use a HIPAA Waiver to acquire the data sets and along with this application we are asking for a waiver of signed consent to link all enrolled patients to the claims data sets. (Note: this is identical to the Control group).

Phase 2: COMPASS-Intervention & COMPASS-Sustain Hospitals

Hospitals which were randomized to the control-arm in Phase 1 of the study will be encouraged to cross over to provide the COMPASS Intervention during Phase 2 of the study. Hospitals that were randomized to the COMPASS Intervention-arm during Phase 1 of the study will be encouraged to continue providing all of the COMPASS Intervention to eligible patients (Sustain Sites). Both the Intervention and the Sustain Sites will provide the same intervention as described in this section. This intervention is nearly identical to the Phase 1 Intervention. Minor changes were made in order to streamline some of the intervention activities based on lessons-learned from Phase 1. The structure, however, remains unchanged: Patients who enter the study through a participating hospital will receive: (1) a follow-up phone call 2 days after being discharged from the hospital, (2) a 7-14 day Advanced Practice Provider visit, (3) a follow-up 30 day phone call, and (4) a follow-up 60 day phone call.

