Appendix 23 - 90d Patient Survey (CATI/ Phone Format)

COMPASS 90 Day Patient Survey

LABEL	VALUE	TEXT	INSTRUCTIONS
INTRO	0=R DOES NOT HAVE Q'NAIRE FOR REFERENCE 1=R DOES HAVE Q'NAIRE FOR REFERENCE 8=DON'T KNOW	I'm going to be asking you a series of questions about [IF NO PROXY: your] [IF PROXY=1 OR 2: FILL R NAME]'s health and activities since NO PROXY: you were PROXY: he/she was hospitalized for stroke or TIA. Most of the questions are on the questionnaire we mailed [NO PROXY: to you] about a week ago. Do you have that in front of you or would you like to go get it? IN: GIVE THE R TIME TO GO GET IT, BUT IF THEY DON'T HAVE OR CAN'T FIND PAPER Q'NAIRE: That's OK, we can complete the call without it. IF NEEDED: TIA stands for transient ischemic attack and is sometimes referred to as a mini-stroke or warning stroke.	
SIS_INTRO	EMPTY	I'd like to start by asking you about the physical problems NO PROXY: you PROXY: he/she may have because of your/his/her stroke (or TIA). I want to know NO PROXY: [from YOUR POINT OF VIEW] how stroke has affected your/his/her physical	

,	
Application	- IRB00035998

Application - IKB00033998			
		function in the past two	
		weeks.	
		I'm going to read a list of tasks and for each one, I'd like you to tell me whether it is not difficult at all, a little difficult, somewhat difficult, very difficult or if the task can't be done at all. IF NEEDED: I'm required to ask all the questions, but	
		please just answer to the	
		best of your ability.	
CICA			
SIS1	1=Not difficult at all	In the past two weeks how	
	2=A little difficult	difficult was it PROXY: for	
	3=Somewhat difficult	him/her to dress the top	
	4=Very difficult	part of your/his/her body?	
	5=Or you could not do this	Would you say	
	activity at all?		
	8=DON'T KNOW		
SIS2	9=REFUSE 1 =Not difficult at all	In the past two weeks, how	
3132	2=A little difficult	difficult was it [for	
	3=Somewhat difficult	him/her]to bathe	
	4=Very difficult	yourself/himself/herself?	
	5=Or you could not do this	Would you say	
	activity at all?		
	8=DON'T KNOW	INTERVIEWER NOTE:	
	9=REFUSE	Bathing oneself does not	
		include getting into the tub.	
SIS3	1 =Not difficult at all	In the past two weeks, how	
	2=A little difficult	difficult has it been [for	
	3=Somewhat difficult	him/her] to get to the toilet	
	4=Very difficult	on time?	
	5=Or you could not do this		
	activity at all?	(Would you say)	
	8=DON'T KNOW		
	9=REFUSE	INTERVIEWER NOTE: For	
		this question we are	
		interested in how quickly	

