		IN NOTE: THIS MEANS ANY PART OF THEIR BODY AFFECTED EVEN IF NOT THEIR HAND. E.G. FACE, LEG, ETC.	
HEALTH_INTRO		The next two questions are about how you perceive or view your general health.	PROGRAMMING: SKIP IF PROXY=1 OR 2
RateHlt	1=poor 2=fair 3=good 4=very good 5=excellent 8=DON'T KNOW 9=REFUSE	Compared to others your age, how would you rate your health since your stroke or TIA? Would you say	PROGRAMMING: SKIP IF PROXY=1 OR 2
PredHlt	1=Stay the same 2=Improve 3=Get worse 8=DON'T KNOW 9=REFUSE	Over the next 3 months, do you think your health is going to:	PROGRAMMING: SKIP IF PROXY=1 OR 2
MRS_INTRO		This next set of questions is asking about the level of assistance you/he/she may or may not need with certain tasks and your/his/her ability to do things since your/his/her stroke or TIA." [IF INTRO=1, FILL]Depending on your responses I may skip some of the questions on the survey you have in front of you.	

Application - IKBOO	033996	1	T
		IF NEEDED: TIA stands for transient ischemic attack and is sometimes referred to as a "mini-stroke" or "warning stroke."	
MRS1	0=NO (GO TO MRS4) 1=YES (GO TO MRS2) 8=DON'T KNOW (GO TO PA _INTRO) 9=REFUSE (GO TO PA_INTRO)	Could you/he/she live alone without any help from another person? This means being able to bathe, use the toilet, shop, prepare or get meals and manage finances. IN: AVOID DK OR REFUSE. ENCOURAGE THE R TO ANSWER YES OR NO.	
MRS2	0=NO (GO TO PA_INTRO) 1=YES (GO TO MRS3) 8=DON'T KNOW (GO TO PA_INTRO) 9=REFUSE (GO TO PA_INTRO)	Can you/he/she do everything that you/he/she were/was doing right before your/his/her stroke, even if slower and not as much?	
MRS3	0=NO (GO TO PA_INTRO) 1=YES (GO TO PA_INTRO) 8=DON'T KNOW (GO TO PA_INTRO) 9=REFUSE (GO TO PA_INTRO)	Are/Is you/he/she completely back to the way you/he/she were/was right before your/his/her stroke?	
MRS4	0=NO (GO TO MRS5) 1=YES (GO TO PA_INTRO) 8=DON'T KNOW (GO TO PA_INTRO) 9=REFUSE (GO TOPA_INTRO)	Can you/he/she walk from one room to another without help from another person? IN NOTE: WALKING FROM ONE ROOM TO ANOTHER WITHOUT THE HELP OF ANOTHER PERSON – INCLUDES WALKING WITH A CANE OR WALKER AS LONG AS THE PERSON DOES IT INDEPENDENTLY.	

Application - IRB00035998		, 	
MRS5	0=NO (GO TO PA_INTRO) 1=YES (GO TO PA_INTRO)	Can you/he/she sit up in bed without any help?	
		, , , , , , , , , , , , , , , , , , , ,	
	8=DON'T KNOW (GO TO		
	PA_INTRO)		
	9=REFUSE (GO TO PA INTRO)		
PA_INTRO	IA_INTROJ	The next few questions are	
_		about the amount of time	

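### The PROMIS Global-10 block of the 90-day phone script has neither a proxy skip nor third-person wording, so in a proxy interview it is unknown whom the answers describe

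*Protocol*

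**What the plan says.** The Phase 1 and Phase 2 descriptions of the 90-day call both allow a proxy: "If the patient prefers s/he can request that a proxy answer questions and provide verbal consent and HIPAA Authorization on her/his behalf". The Informed Consent section adds that the study records whether patient or proxy supplied the data, and that proxies should seldom be needed in a population discharged home.

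The phone script in Appendix 23 adapts to a proxy from its opening, which substitutes the patient's name: "IF PROXY=1 OR 2: FILL R NAME]'s health and activities". Several later blocks carry the instruction "PROGRAMMING: SKIP IF PROXY=1 OR 2".

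The protocol lists Global-10 under data collected for ancillary studies: "At the 90 day survey, we will also use the PROMIS Global-10 instrument that assesses general domains of health and functioning". It is also tabulated as a patient outcome for Phase 2, with Appendix 23 as its source. In the script the block opens with "These last few questions are about your health and how you have been feeling", begins with "In general, would you say your health is" and ends with "In the past 7 days, how would you rate your pain on average". None of its rows has a proxy instruction.

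**The concern.** A patient-reported score is interpretable only if it is known whose state it reports. A proxy who has been answering about the patient is suddenly asked about 'your' health, quality of life, mood, fatigue and pain. The proxy may answer personally or go on answering for the patient, and either answer is stored in the patient's Global-10 fields.

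Two things make this more than loose wording. First, the script elsewhere treats the same constructs as ones a proxy should not report. Second, the protocol describes Global-10 as resembling the primary outcome, so a reader will naturally set it beside SIS-16. In a proxy interview the two scores may describe different people. The phone screener has branches for patients whose stroke prevents them from talking on the phone, so proxy interviews are probably concentrated among more impaired patients.

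**Working it through.** No formula applies. The check is a row-by-row reading of Appendix 23 for two devices: a proxy skip, and third-person alternatives.

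| Block in Appendix 23 | Third-person forms | Proxy skip |
|---|---|---|
| SIS-16 | yes | no |
| Self-rated and predicted health | no | yes |
| Modified Rankin questions | yes | no |
| Walking | yes | no |
| Mood (two items) | no | yes |
| MoCA | no | yes |
| Medication adherence | no | yes |
| Blood pressure, usual provider, therapy | yes | no |
| Falls and hospitalization | yes | no |
| PROMIS fatigue | no | yes |
| Satisfaction with care | yes | no |
| Community resources | mostly | no |
| Education | yes | no |
| **Global-10 introduction and ten items** | **no** | **no** |

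1. **Count.** Of the ten Global-10 items, 10 have no skip and 10 have no he/she or his/her form. The introduction also has neither.

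2. **Is it a loss in text extraction?** Unlikely. The skip text survives on the other skipped blocks. The education item directly above the Global-10 introduction still reads "What is the highest grade or level of school that you/he/she have/has completed". The Global-10 items also lack the don't-know and refuse codes that nearly all other items have. That suggests an instrument added without being fitted to the survey's conventions.

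3. **Could the fatigue skip cover it?** No. Both introductions are labelled PROMIS_INTRO, but in the fatigue block the skip is repeated on the introduction and on each of the four items. It is therefore a row-level instruction, and no Global-10 row has it. The shared label is a small defect in itself, because the branches from the readmission items go to a label that occurs twice.

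4. **Conflict with the script's own rule.** The script skips self-rated health for proxies but asks Global01 (general health) of anyone. It skips mood but asks Global10 (emotional problems). It skips PROMIS fatigue but asks Global08 (fatigue).

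5. **What the proxy flag settles.** It identifies interviews in which a proxy answered. It does not show whether that person was describing the patient or himself or herself.

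6. **Size.** A shift in the overall mean would equal the proxy share times the average score gap between the stored and the true patient answers. The documents supply neither input. With purely assumed values, a gap of 10 T-score points gives 0.01 × 10 = 0.1 at a 1% share, 0.05 × 10 = 0.5 at 5% and 0.15 × 10 = 1.5 at 15%. The fifteenfold spread comes entirely from the assumed share, and the sign and size of the gap are assumed as well. This is not an estimate.

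**The case against.** The strongest reply is that the wording is ambiguous rather than wrong. The call opens by naming the patient, and a proxy answers a long run of items about the patient before reaching Global-10. The consent text also describes a proxy as someone who may support the patient in responding, so the patient may be taking part. Bare 'you' and 'your' occur in several community-resource items that proxies answer, where the patient is plainly meant. All of this stands, and it means that some proxy answers probably do describe the patient.

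A reader might infer more: that every proxy rates his or her own health, that no proxy record is valid, and that Phase 2 means are therefore biased upward. The documents do not support this. The referent is unknown, which is different from being known to be the proxy. The direction is not settled either: the Background section reports poorer mental health, less social contact and more depression risk among caregivers, and several Global-10 items cover those domains.

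It is also fair that exposure is limited. Proxy need is described as unlikely, and mean stroke severity in the source population is 3.2 on a 0 to 42 scale. The protocol specifies no Global-10 analysis, and the supplied SAP covers only claims and mortality. No planned estimate is shown to be distorted.

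The omission itself survives these points. An unknown referent is enough to make a proxy-answered record unusable as a patient report, and the supplied documents give no rule for such records.

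**Conclusion.** The defect is real and confined to one block. Read as written, the script stores answers of unknown referent in a listed Phase 2 patient outcome, contrary to its own handling of comparable items. What can be said is that no proxy-answered Global-10 record can be known to describe the patient. How many such records exist, and which way they would move a mean or a correlation with SIS-16, cannot be derived from the documents.

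The conclusion rests on the script having been run as printed. If interviewers were trained to rephrase these items for proxies, the problem would shrink, but the supplied documents do not say so. The primary outcome and the listed secondary outcomes are not touched. This is worth correcting because it is cheap, not because it threatens the trial's main result.

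**What to change.** **Data already collected.** Phase 2 enrolment was planned to end in January 2019, so a data rule is the remedy that still matters. First confirm what PROXY=1 and PROXY=2 mean, since the definitions are not visible in the supplied text. Then treat Global01 to Global10 as missing whenever the flag shows that a proxy answered. Report the number of records affected.

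**Any further use of the script.** Add the proxy skip already used for the fatigue items to the Global-10 introduction and all ten items. Give that introduction its own label, so that the branch from the readmission items has one target.

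**Cost.** One cleaning rule on a recorded variable, and a few programming entries. There will be slightly fewer Global-10 records, with the loss probably concentrated in more impaired patients. This missingness is not random, so any Global-10 report should state that it describes self-responders only.

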Appendix 24 - 90d Patient Survey (Full Survey Mailed with the 80 day letter)

This is a copy of the questions you will be asked during the phone call. You do not have to fill this out, but can if you would like to prepare for the call. It will be helpful to have this copy with you during the call.

A. PHYSICAL CHALLENGES SINCE YOUR HOSPITAL VISIT: These questions are about the physical problems you may have experienced recently because of your stroke or TIA. ("TIA" stands for *transient ischemic attack* and is sometimes referred to as a *mini-stroke*, *warning stroke*, *brain episode*, or *brain bleed*.) We want to know from your point of view how your stroke or TIA has affected your physical function in the past 2 weeks?

In the past 2 weeks, how difficult was it to	Not difficult at all	A little difficult	Somewhat difficult	Very difficult	Could not do at all
Dress the top part of your body?					
Bathe yourself?					
Get to the toilet on time?					
Control your bladder (not have an accident)?					
Control your bowels (not have an accident)?					
Stand without losing balance?					
Go shopping?					
Do heavy household chores (e.g. vacuum, laundry or yard work)?					
Stay sitting without losing your balance?					
Walk without losing your balance?					
Move from a bed to a chair?					
Walk fast?					
Climb one flight of stairs?					
Walk one block?					
Get in and out of a car?					
Carry heavy objects (e.g. bag of groceries) with your affected hand?					

	ENERAL HEALTH Q eneral health.	UESTIONS: These	questions are	about how you p	erceive or view	your
1.	Compared to others scale between 1 and				ur stroke or TIA	using a
	Poor	Fair	Good	Very Good	Excellent	
2.	Over the next 3 mon Improve Stay the sa Get worse	-	3 ur health is goi	ng to:	5	
as	EVEL OF ASSISTAN ssistance you may or roke (or TIA).					
1.	Could you live alone use the toilet, prepa ☐ Yes ☐ No				s being able to	bathe,
2.	Can you do everythinot as much? ☐ Yes ☐ No	ng that you were do	ing right before	e your stroke (or	TIA), even if slo	wer and
3.	Are you completely ☐ Yes ☐ No	back to the way you	were right befo	ore your stroke (or TIA)?	
4.	Can you walk from o ☐ Yes ☐ No	one room to another	without help fr	om another pers	on?	
5.	Can you sit up in be ☐ Yes ☐ No	d without any help?				
						2

haves	SICAL ACTIVITY QUESTIONS: The next few questions are about the amount of time you spent walking in the last 7 days. g the last seven days:
1.	Did you walk continuously for at least 10 minutes on any day? ☐ Yes ☐ No
2.	On how many days did you walk continuously, for at least 10 minutes, for recreation, exercise, or to get to or from places?
	Enter a number from 0 - 7:
3.	On days that you walked for at least 10 minutes, how much total time per day did you spend walking?
	Enter a number minutes
4.	What is the total amount of time you spent walking over the last seven days? Enter a number minutes
	D QUESTIONS: The next 2 questions are about your mood over the past 2 weeks. the past two weeks , how often have you been bothered by any of the following problems:
1. Lit	tle interest or pleasure in doing things:
	 □ Not at all □ Several days □ More than half of the days □ Nearly every day
2. Fe	eling down, depressed, or hopeless:
	□ Not at all □ Several days □ More than half the days □ Nearly every day
	rviewer will now ask you some questions to assess your memory.
The inte	rviewer will now ask you some questions to assess your memory.
	re not printed on the survey because they need to be asked over the phone.

	EDICATION QUESTIONS: The next 4 questions are about medications you take. Think about w you have taken your medications during the past 4 weeks when answering these questions.
1.	Do you ever forget to take your medicine? ☐ Yes ☐ No
2.	Are you careless at times about taking your medicine? ☐ Yes ☐ No
3.	Sometimes if you feel worse when you take the medicine, do you stop taking it? ☐ Yes ☐ No
4.	When you feel better, do you sometimes stop taking your medicine? ☐ Yes ☐ No
i. SE yo	ELF-MANAGEMENT & USE OF CARE QUESTIONS: These next questions are about checking ur blood pressure and your usual health care provider.
1.	Do you check your blood pressure at home ? ☐ Yes ☐ No
	1a. If yes, how frequently do you check your blood pressure? ☐ Daily ☐ Weekly ☐ Monthly
	1b. What was the value of your last blood pressure? Please provide the systolic (top number) and diastolic (bottom number).
	(systolic) /(diastolic)
	1c. Who took this blood pressure measurement? ☐ You ☐ A healthcare professional ☐ A family member ☐ Someone else: (please specify)
2.	Is there a particular doctor's office, health center, or other place that you usually go if you are sick and need advice about your health? ☐ Yes ☐ No
	2a. If yes, have you visited a doctor or nurse from that office, health center, or other place since you were discharged from the hospital after your stroke (or TIA)? ☐ Yes ☐ No

3.a. Since you were discharged home after your stroke (or TIA), have you received any services from:		3.b. If yes, did you receive services in:			
		Your home?	Outpatient clinic?	Both?	
i. A physical therapist?	☐ Yes ☐ No				
ii. An occupational therapist?	□ Yes □ No				
iii. A speech therapist?	□ Yes □ No				
fall? □ Yes	from the l tinjured a	hospital after you	ir stroke (or TIA), have the doctor or emerge	ncy room due to	
	□ No				
1c. If yes, how many	times hav	ve you fallen?			
Enter a number					
2. Since you were discharged reason?	from the	hospital, have yo	u been hospitalized o	vernight for any	
□ Yes □ No					
2a. If yes, how many	times hav	ve you been in the	e hospital overnight fo	or any reason?	

	ng the past 7 days how often you:	Not At all	A little b	t Sor	newhat	Quite	e a bit	Very much
1.	Felt tired or fatigued?					1		
2.	Had trouble starting things because you were tired?					[2	-
n the	e past 7 days:	Not At all	A little b	t Soi	mewhat	Quite	e a bit	Very much
3.	How run-down did you feel on average?		0					
4.	How fatigued were you on average?							
Γhink	oke (or TIA). king about the care you have re	eceived for yo	our stroke	(or TIA) recove	ry sind	ce you v	vere
str Think	*************************************	eceived for yo often did you	r physicia	(or TIA ns, nur Never	ses, and	other	ce you v healthc Usually	are provide
str Fhink disch	king about the care you have re	often did you	r physicia	ns, nur	ses, and	other	healthc	are provide
str Think disch	king about the care you have re narged from the hospital, how o	often did you	r physicia	Never	ses, and	other	Healthc Usually	are provide Always
str Think disch	king about the care you have re narged from the hospital, how o l. Explain things in a way that understand?	was easy to	r physicia	Never	Someti	other	Healthc Usually	are provide
str Think disch	ing about the care you have re narged from the hospital, how on the hospital, how on the hospital, how on the hospital, how on the hospital has a way that understand?	was easy to	r physicia	Never	Someti	other	Usually	Always
str Fhink Idisch	ing about the care you have reparted from the hospital, how consider the hospital from the hospital, how consider the hospital from the ho	was easy to	r physicia	Never	Ses, and	other	Usually	Always

6

I. FATIGUE QUESTIONS: The next few questions are about feelings of tiredness or fatigue.

K. COMMUNITY RESOURCES QUESTIONS: These next questions are about any community services you have used since your stroke (or TIA).

Thinking back since you were discharged from the hospital after your stroke (or TIA), have you used any of the following services to assist you with your care?

	d any of the following services to assist you with your care?	Yes	No
1.	Adult day care programs or other services for social support or recreation for stroke (or TIA) survivors	0	
2.	Community services or classes to help with your ability to speak, read, or write (e.g. Aphasia Support Group)		0
3.	Counseling services or therapy for stress or depression (e.g. CareNet counseling)	0	
4.	Any programs that promote healthy living, like classes on diet or managing diabetes, chronic pain, problems with breathing, or high blood pressure		
5.	Exercise classes that are open to the general public, like ones offered at a church or fitness center (e.g. Silver Sneakers, Silver & Fit, Hospital wellness programs)	0	
6.	Programs to help you quit smoking		
7.	Falls prevention program that teaches you how to improve your balance and strength so you don't fall		
8.	Programs that provide meals (delivered to your house or a central location like a church or community center)	П	
9.	A support group for stroke (or TIA) survivors		
10	. Medication assistance or management services to help pay for the medications or to help understand and manage the medications		
11	. Transportation services to get you to your healthcare appointments or community activities		

12. Support services for your family/caregivers						
13. Other services? If yes, describe:						
L EDUCATION QUESTION:						
L. EDUCATION QUESTION: 1. What is the highest grade or level of school that you have completed? 8 th grade or less Some high school, but did not graduate High school graduate or GED Some college or 2-year degree 4-year college graduate More than 4-year college degree						
M. PRIMARY CAREGIVER : Please verify who is the family member, friend, or nei have helped you with activities such as shopping and transportation since your received						
THIS IS THE END OF THE SURVEY - THANK YO	U!					
We are sorry to have missed you on the phone. We value your response and hope you will complete this brief questionnaire. Please return it within 5 days in the envelope provided.

A. PHYSICIAL CHALLENGES SINCE YOUR HOSPITAL VISIT: These questions are about the physical problems you may have experienced recently because of your stroke or TIA. ("TIA" stands for *transient ischemic attack* and is sometimes referred to as a *mini-stroke*, *warning stroke*, *brain episode*, or *brain bleed*.) We want to know from your point of view how has your stroke or TIA affected your physical function in the past 2 weeks?

In the past 2 weeks, how difficult was it to	Not difficult at all	A little difficult	Somewhat difficult	Very difficult	Could not do at all
Dress the top part of your body?					
Bathe yourself?					
Get to the toilet on time?					
Control your bladder (not have an accident)?					
Control your bowels (not have an accident)?					
Stand without losing balance?					
Go shopping?					
Do heavy household chores (e.g. vacuum, laundry or yard work)?					
Stay sitting without losing your balance?					
Walk without losing your balance?					
Move from a bed to a chair?					
Walk fast?					
Climb one flight of stairs?					
Walk one block?					
Get in and out of a car?					
Carry heavy objects (e.g. bag of groceries) with your affected hand?					

1

B.	GENERAL HEALTH QUESTIONS:	These questions are about how you perceive or view your
	general health.	

1. Compared to others your age, how would you rate your health since your stroke or TIA using a scale between 1 and 5 with 1 being "poor" and 5 being "excellent?"

Poor	Fair	Good	Very Good	Excellent
1	2	3	4	5

2.	Over the next	3 months,	do	you think	your	health	is	going 1	to:
----	---------------	-----------	----	-----------	------	--------	----	---------	-----

☐ Improve

☐ Stay the same

☐ Get worse

3.	What was the value of your last blood pressure?	Please provide the systolic (top number) and
	diastolic (bottom number).	

(systolic) /	(diastolic)
(SVSIDIIC) /	totasioner

THIS IS THE END OF THE SURVEY - THANK YOU!

The website for this study can be accessed at: https://www.nccompass-study.org/

If you have any questions about the study, please contact our project manager at [name].

If you have any questions about your rights as a research study participant, you may contact, anonymously if you wish, the Institutional Review Board. Their job is to protect your rights and welfare as a research participant. They have reviewed and approved this study. You can reach them at [contact] or by email to [contact].

